Study Design

Patients

The open-labeled trial is conducted at the Kaohsiung Veterans General Hospital, Kaohsiung Medical University Hospital and Kaohsiung Chang Gung Memorial Hospital in Taiwan in accordance with the principles of good clinical practice from the Declaration of Helsinki. The study protocol was approved by the Ethics Committees in each study center. All patients will be given written informed consent before participating in the study. Patients between the ages of 20 and 80 years with clinical symptoms of acid regurgitation, heart burn, or feeling of acidity in the stomach, who have Barrett's Esophagus proven by histology confirmation of esophageal metaplastic mucosa with length equal to or longer than 1 centimeter will be enrolled. Criteria for exclusions include (1) pregnancy, (2) coexistence of serious concomitant illness (for example, decompensated liver cirrhosis and uremia), (3) previous gastric surgery, (4) allergy to esomeprazole, (5) presence of dysplastic esophageal mucosa, and (6) equivocal endoscopic diagnosis of Barrett's esophagus (e.g., esophageal metaplastic mucosa less than 1 cm).

Study Design and Randomization

Eligible patients will be randomly assigned to receive either (1) on-demand PPI

therapy (40 mg of esomeprazole [Nexium, AstraZeneca, Sodertalje, Sweden] daily for 8 weeks, and then on-demand esomeprazole 40 mg daily if symptoms recurred.) or (2) continuous PPI therapy (40 mg of esomeprazole daily for 48 weeks). Randomization will be carried out with the use of a computer-generated list of random numbers. An independent staff member assigns the treatments according to consecutive numbers that are kept in sealed envelopes. The participants in the on-demand group will be instructed to take esomeprazole 40 mg daily for consecutive three days whenever reflux symptoms bothered them. If patients have obvious reflux symptoms soon after discontinuing PPI therapy twice or more, on-demand PPI treatment could be switched to continuous PPI use. In the continuous PPI therapy group, the participants take esomeprazole 40 mg daily no matter symptoms develop or not. All the participants are instructed to take esomeprazole 30 minutes before breakfast.

They are requested to complete a Chinese GERDQ on enrollment. The total score of GERD symptoms will be recorded. Each participant should complete diary cards during the study period. They return to the clinics for drug refills and evaluation of reflux symptoms every month. The participants are asked to hand in daily symptom records at each visit, and to report the number of esomeprazole tablets taken per 4-week period. Follow-up endoscopy with biopsy for esophageal mucosal metaplasia

will be performed at the end of 48 weeks.

Endoscopy

Endoscopy is performed on enrollment, and the esophagus is carefully evaluated.

Endoscopic suspected esophageal metaplasia (ESEM) is defined as a tongue-shaped projection of salmon-colored mucosa from the esophagogastric junction (the point where the proximal end of the gastric folds meets the tubular esophagus). All of the four quadrants of ESEM will be sampled every 2 cm. The Barrett's esophagus is defined as gastric or intestinal metaplastic change of distal esophageal epithelium confirmed by biopsy. The grade of Barrett's esophagus is scored according to the Prague C & M criteria. All subjects with biopsy-proven Barrett's esophagus will be further categorized into long-segment Barrett's esophagus and short-segment Barrett's esophagus. Long-segment Barrett's esophagus is defined as the maximal length of metaplastic columnar epithelium over distal esophagus equal to or more than 3 cm, and short-segment Barrett's esophagus is defined as the extension of columnar epithelium over distal esophagus less than 3 cm. Erosive esophagitis will be scored using the Los Angeles classification system. Hiatus hernia is defined as a distance between the esophagogastric junction and the diaphragmatic hiatus equal to or more than 1 cm.

H pylori examination

Two biopsy specimens are taken from the lesser curvature sites of the antrum, and another two from the corpus. They will be fixed in 10% buffered formalin, embedded in paraffin, and sectioned. The sections, 4- μ m thick, will be stained with a haematoxylin and eosin stain and a modified Giemsa stain to observe the presence of curved rod shape bacteria on the mucosal surface. Biopsy specimens will be assessed by histopathologists, who are blinded to patient status and the results of other laboratory tests.

Questionnaire

A standardized data-collection form for medical history and demographic data will be obtained from each patient on enrollment, including age, sex, body mass index (BMI), medical histories, histories of smoking, alcohol, coffee and tea consumption. Smoking is defined as consumption of cigarettes 1 pack or more per week. Coffee or tea consumption is defined as drinking 1 cup or more per day.

Chinese GERDQ is a validated symptom questionnaire for the diagnosis and severity evaluation of gastroesophageal reflux disease. In the scoring system, the evaluated symptoms include acid regurgitation, heartburn and feeling of acidity in the stomach. The severity of symptoms in the questionnaire are graded on a five-point

Likert scale as follows: 1 (none; no symptoms); 2 (mild: symptoms can be easily ignored); 3 (moderate: awareness of symptoms but easily tolerated); 4 (severe: symptoms sufficient to cause an interference with normal activities); 5 (incapacitating: incapacitating symptoms with an inability to perform daily activities or work), and frequency of symptoms are graded as follows: 1 (none in the past year); 2 (less than once per month); 3 (\geq once per month); 4 (\geq once per week); 5 (\geq once daily). A cut-off score of ≥ 12 is used to make the diagnosis of symptomatic GERD.

Genotyping of CYP2C19

Blood sampling for genotyping of CYP2C19 will be carried out after endoscopy for the subjects who provides informed consent for genetic study. The *CYP2C19* genotype is determined using the polymerase chain reaction-restriction fragment length polymorphism (PCR-RFLP). Genotypes are classified into three groups: homEM (*CYP2C19*1/CYP2C19*1*); hetEM (*CYP2C19*1/CYP2C19*2*) and (*CYP2C19*1/CYP2C19*3*); PM (*CYP2C19*2/CYP2C19*2*, *CYP2C19*2/CYP2C19*3*, and *CYP2C19*3/CYP2C19*3*).

End Points

The primary outcome measures are (1) histological progression of metaplastic

esophageal epithelium at 48 weeks, and (2) total symptom days within the 48-week study period. The secondary outcome measure is total PPI consumption during the 48-week study period. Histological progression of metaplastic esophageal epithelium is defined as (1) progression from gastric metaplasia into intestinal metaplasia, low grade-dysplasia or high-grade dysplasia, or (2) progression from intestinal metaplasia into low-grade or high-grade dysplasia.

Statistics

Our study is designed as a non-inferiority trial. Sample size was calculated from numbers needed to show that on-demand therapy is non-inferior to continuous therapy based on the proportion of patients who would discontinue the study prematurely because of unsatisfactory therapy. The hypothesis for sample size calculations are based on 94% on-demand therapy continuation rate and 92% continuous therapy continuation rate. On-demand therapy is defined as non-inferior to continuous therapy if the upper bound of the two-sided 90 % CI for the difference in proportions (on-demand minus continuous) is less than 10 %.

With a sample size of 78 patients in each treatment group, a one-sided test of proportions at the 5 % level had 90 % power to reject the hypothesis that on-demand therapy is inferior to continuous treatment. With an assumption of 10 % non-evaluable

patients and 10% non-eligible patients for randomization, it was calculated that 196 patients would be required in the initial enrollment to yield sufficient power.

Statistical analysis will be performed using the Statistical Program for Social Sciences (SPSS 19.0 for windows). Univariate analysis is performed by Student's t test for continuous variables and χ^2 test is used for categorical variables. $P < 0.05$ is considered statistically significant and all reported p values are two-sided.

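### The baseline GERDQ total is recorded but not used when total symptom days are compared; adjusting for it would be a free gain in precision (minor)

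*Combined protocol and SAP*

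**What the plan says.** All references are to the combined protocol and SAP.

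- **Patients.** Entry requires histologically proven Barrett's esophagus of at least 1 cm in patients "with clinical symptoms of acid regurgitation, heart burn, or feeling of acidity in the stomach". No severity, frequency or score threshold is attached to the symptoms.
- **Study Design and Randomization.** On the questionnaire: "They are requested to complete a Chinese GERDQ on enrollment". Then: "The total score of GERD symptoms will be recorded". Symptoms during the trial come from a different source: "Each participant should complete diary cards during the study period". The allocation list is computer-generated, and no stratification is described.
- **Questionnaire.** Three symptoms are each graded 1 to 5 for severity and 1 to 5 for frequency. The section adds: "A cut-off score of ≥ 12 is used to make the diagnosis of symptomatic GERD". It does not say how the grades combine into a total.
- **End Points.** The second of the two primary outcomes is "total symptom days within the 48-week study period". The GERDQ score is not an endpoint.
- **Statistics.** "Univariate analysis is performed by Student's t test for continuous variables", with a chi-square test for categorical variables. No covariate is named for any outcome. Symptom days are not mentioned individually, so the t test applies to them as a continuous variable.

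**The concern.** The trial collects one measure of symptom burden before treatment and then makes no planned use of it. Half of the GERDQ items grade how often symptoms occur, and the endpoint counts days with symptoms, so some association between the two is plausible. Where it exists, an unadjusted t test leaves explainable between-patient variation in the error term. The interval for the difference in symptom days is then wider than it need be. The estimate also carries any chance difference in baseline symptoms between the arms that adjustment would have removed.

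At stake is the precision of one primary comparison. Prespecification matters as well: the trial is open-label and symptom days are reported by patients, so a covariate chosen after the data are seen would be open to the charge of selection.

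**Working it through.** **1. The plan's own sample size, and whether it depends on this point.** Inputs from Statistics: continuation 94% on-demand and 92% continuous, margin 10 points, one-sided 5%, power 90%. With the unpooled normal approximation:

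n = (1.645 + 1.282)² × (0.94 × 0.06 + 0.92 × 0.08) / (0.10 + 0.02)² = 8.57 × 0.130 / 0.0144 ≈ 77.3, rounded up to **78 per group**, as stated (power at 78 is 90.2%).

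For enrollment, 156 / 0.80 = 195, against 196 stated. Neither GERDQ nor symptom days enters this calculation, so adjusting symptom days leaves the 78 unchanged.

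**2. Gain from adjustment.** Let r be the within-arm correlation between baseline GERDQ total and total symptom days. The documents do not give r, so 0.3 to 0.6 is an assumption. Adjustment multiplies the variance of the treatment difference by (1 − r²), which is equivalent to multiplying the sample by 1/(1 − r²).

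For a sense of scale, take a two-sided 5% test with 78 per arm. The difference detectable with 80% power without adjustment is (1.960 + 0.842) × √(2/78) = 0.449 SD. With adjustment it is 0.449 × √(1 − r²).

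| Assumed r | Variance removed (r²) | Sample equivalent 1/(1 − r²) | Effective n per arm | Detectable difference (SD) | Power at 0.449 SD |
|---|---|---|---|---|---|
| none used | 0% | 1.00 | 78 | 0.449 | 80% |
| 0.2 | 4% | 1.04 | 81 | 0.440 | 82% |
| 0.3 | 9% | 1.10 | 86 | 0.428 | 84% |
| 0.5 | 25% | 1.33 | 104 | 0.389 | 90% |
| 0.6 | 36% | 1.56 | 122 | 0.359 | 94% |

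The 0.2 row shows what is left if the score predicts less well than assumed. The plan gives no SD for symptom days, so none of this can be put in days.

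**3. Is the total defined well enough to use?** Both natural scoring rules were tried, with the two other symptoms absent (grade 1 for severity and frequency).

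- One mild symptom (2), less than monthly (2): sum (2+2)+(1+1)+(1+1) = 8; product 2×2 + 1×1 + 1×1 = 6. Both are below 12.
- One moderate symptom (3), weekly (4): sum (3+4)+(1+1)+(1+1) = 11; product 3×4 + 1 + 1 = 14. This patient is below the cut-off under one rule and above it under the other.

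The scoring rule must therefore be written down before the score serves as a covariate or defines a subgroup.

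**The case against.** The strongest reply is that nothing here is invalid. Allocation is randomized, so an unadjusted comparison of a count made after randomization is unbiased, and the test's error rate already allows for chance imbalance. That stands. Only precision is lost.

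It can also be said that the gain is purely assumed. The documents give no correlation, no SD and no distribution of scores. They describe no period off acid suppression before the enrollment questionnaire, so in patients already treated the score may predict later symptom days poorly. That stands too, and it limits the claim to a range. It does not argue against adjusting: a weak covariate costs about one degree of freedom, while a useful one narrows the interval.

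A reader might infer three stronger things, which the documents do not support.

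- *That symptom days are compared with no baseline measure available.* A baseline total is recorded; only its planned use is missing.
- *That patients with trivial symptoms enter, make the arms look alike and undermine the non-inferiority conclusion.* The entry wording permits scores below 12, but the share of such patients is unknown. The plan's only non-inferiority margin concerns premature discontinuation for unsatisfactory therapy; symptom days have no margin. Unexplained variance also widens an interval, which under an interval-based rule makes non-inferiority harder to show.
- *That the cut-off of 12 ought to be an entry rule.* The plan offers it as a diagnostic threshold for symptomatic GERD. The population is histologically defined and the first primary outcome is histological, so entry without a score threshold is a defensible choice.

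**Conclusion.** The point holds as a minor one: a free improvement, not a flaw in validity. A baseline symptom score is collected and then left out of the comparison of a primary outcome to which it is plausibly related. Under the assumed correlation of 0.3 to 0.6, the unadjusted test forgoes a variance reduction of 9% to 36%. At a correlation of 0.2 the loss is 4%. The size rests wholly on that assumption. The absence of planned adjustment, and of a scoring rule, rests on the text itself. The conclusion does not extend to bias, to the discontinuation-based non-inferiority test, to the sample size or to eligibility.

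**What to change.** In Statistics, replace the t test for this outcome with a prespecified model. The main comparison of total symptom days would be a regression (for example ANCOVA) with treatment arm and baseline GERDQ total as covariate, reporting the adjusted difference with its confidence interval. In Questionnaire, state whether the total is the sum or the product of the severity and frequency grades, and what the cut-off of 12 is for.

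An analysis of patients scoring 12 or more may be added as supportive only. It should not have to agree in direction with the main result. If the regimens are truly equal and a share q of patients falls in the subset (assumed, equal variances), the two estimates correlate at √q and differ in sign with probability arccos(√q)/π. That is 10% at q = 0.9, 18% at q = 0.7 and 25% at q = 0.5. Such a rule would often block a sound conclusion over a negligible difference.

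The cost is wording. The score is already part of the enrollment procedures, the 78 per group and the entry criteria stay as they are, and the model uses one more degree of freedom. The plan would also need a sentence on how a missing baseline score is handled. The supportive analysis would have fewer patients and a wider interval.

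### The only secondary outcome, total PPI use, rests on patients' own tablet reports in an open-label trial, with no count of returned tablets and a reporting unit that does not match the visit unit

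*Combined protocol and SAP*

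**What the plan says.** All references are to the combined protocol and SAP.

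- **Outcome.** End Points: "The secondary outcome measure is total PPI consumption during the 48-week study period". No other secondary outcome is named.
- **Visits.** Study Design and Randomization: "They return to the clinics for drug refills and evaluation of reflux symptoms every month".
- **How tablets are recorded.** The same paragraph asks patients "to report the number of esomeprazole tablets taken per 4-week period".
- **Other records.** "Each participant should complete diary cards during the study period". What patients bring in is described only as symptom data: "The participants are asked to hand in daily symptom records at each visit".
- **End of follow-up.** Repeat endoscopy with biopsy "will be performed at the end of 48 weeks". No final tablet report is mentioned there.
- **Blinding.** Study Design, Patients: "The open-labeled trial is conducted at the Kaohsiung Veterans General Hospital".

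The document gives no visit schedule in weeks, no visit window, no comparison of tablets dispensed with tablets returned, no formula for the 48-week total and no rule for a missing report.

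**The concern.** This outcome shows how much drug the on-demand strategy saves, and two features of its measurement are weak.

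First, the count is whatever the patient says it is. Patients in the continuous arm know that they are meant to take a tablet every day, so full intake is the expected answer. Missed tablets that are reported as taken raise that arm's total and inflate the saving. Patients already attend for refills, so a more direct count is within reach, but none is planned.

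Second, the visit unit and the reporting unit differ, and 48 weeks is not the same number of each. Three hospitals have to interpret the text. On one reading of it, some days never enter the total. Days lost after week 8 cost the continuous arm more tablets than the on-demand arm, which would understate the saving.

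**Working it through.** **The plan's own figure.** The document states no number of visits or tablet reports to reproduce. Its one design calculation is the sample size (Statistics): "a one-sided test of proportions at the 5 % level had 90 % power" with 78 per group. The inputs are continuation rates of 94% (on-demand) and 92% (continuous) and a 10-point margin:

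- Variance term: 0.94 × 0.06 + 0.92 × 0.08 = 0.130.
- n = 0.130 × (1.645 + 1.282)² / (0.10 + 0.02)² = 77.3, rounded up to 78.

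This reproduces, and tablet use does not enter it.

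**Self-report.** Full intake in the continuous arm is 48 × 7 = 336 tablets. Let m be the share missed but reported as taken (an assumption; the document gives no figure). The arm is overstated by 336m:

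- m = 5%: 16.8, about 17 tablets.
- m = 10%: 33.6, about 34 tablets.
- m = 20%: 67.2, about 67 tablets.

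The saving is overstated by the same amounts if the on-demand arm reports accurately. That arm also takes a daily tablet for its first 56 days. If it over-reported by the same share in that phase, 56m would cancel and 280m would remain: 14 tablets at 5% and 56 at 20%.

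For scale, let f be the average share of days with a tablet in the on-demand arm after week 8 (assumed 10% to 50%). With full intake reported in the continuous arm, the reported difference is 336 − (56 + 280f) = 280(1 − f), which is 252 tablets at f = 10%, 210 at 25% and 140 at 50%.

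**Units.** 336 / 28 = 12 four-week periods. A calendar month averages 365.25 / 12 = 30.44 days, so 336 days is 11.04 months.

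| Reading | Days covered | Days uncounted |
|---|---|---|
| Month means four weeks: 12 visits, 12 reports | 336 | 0 |
| Calendar months, each report covers all days since the last visit | 11 × 30.44 = 334.8 | 1.2, or none if tablets are also reported at week 48 |
| Calendar months, each report covers 28 days, no report at week 48 | 11 × 28 = 308 | 28 (8.3%) |

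On the third reading, the gaps are 30.44 − 28 = 2.44 days in each of 11 intervals (26.8 days) plus 1.2 days at the end. A gap before day 56 does not change the difference, because both arms are then on a daily tablet. If u uncounted days fall among the 280 after week 8, the difference loses u(1 − f) out of 280(1 − f). The shrinkage is therefore u/280 at any constant f:

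- Each report covers the 28 days before the visit: two gaps (4.9 days) precede day 56, so u = 23.1 and the shrinkage is 8.3%.
- Each report covers the first 28 days of the interval: one gap (2.4 days) precedes day 56, so u = 25.6 and the shrinkage is 9.1%.

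The difference stays positive for any f below 100%.

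**The case against.** The strongest reply concerns the units. A monthly visit mentioned beside a four-weekly tablet report is most naturally read as a four-weekly visit. The other durations agree: 8 weeks is two periods and 48 weeks is twelve. On that reading every day is counted. A report could also cover the whole time since the last visit, and the week-48 endoscopy is a contact at which the count could close. An analyst could also scale four-weekly figures up to 48 weeks. All of this stands, so the third row of the table is a possibility and not what the plan prescribes.

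A reader might infer that one of the twelve periods is lost, with a 10% shrinkage. The text does not support that. The loss needs three unstated conditions together, and even then the uncounted days are scattered and partly fall before week 8. A 10% shrinkage would require a whole four-week block after week 8 to go missing (28/280). A reader might also infer that a report spanning the week-8 change of regimen distorts the result. It does not, because the outcome is a total over 48 weeks and not use by phase.

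On self-report, the reply is that patient recall is a common measure, that diary cards are kept throughout, and that returned-tablet counts err too when tablets are discarded or packs are not brought back. The last point stands. The diary point helps little, since the document does not say that the cards record tablets. The share of missed tablets is assumed, so the size of this error is illustrative.

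**Conclusion.** The point holds as a cheap improvement to how the secondary outcome is measured. Its firmer half is the unverified self-report, which needs no particular reading of the calendar. An overstatement of about 17 to 67 tablets of 336 follows if 5% to 20% of tablets are missed and unreported in the continuous arm and on-demand reports are accurate. Neither condition can be checked with the records described.

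The mismatch of units is mostly a matter of wording. At worst it leaves 28 of 336 days uncounted and shrinks the difference by about 8% to 9%, in the opposite direction to the self-report error and without reversing the comparison. On the four-week reading it costs nothing.

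It would go too far to say that the planned data are bound to contain two opposing errors: the missing days are not shown to occur, and the over-reporting is plausible but unmeasured. Nothing here touches the primary outcomes, the non-inferiority margin or the sample size.

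**What to change.** - Define total PPI use as tablets dispensed minus tablets returned, summed over the refill visits already planned and closed with a final count at week 48.
- Keep the patient's report as a cross-check, and as the backup value when a pack is not returned. State how a period with neither is handled.
- Ask for tablets taken since the last visit, so that the total is complete whatever the interval between visits.
- Reconcile the monthly visits with the four-weekly reports so that all three hospitals work to one unit.

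The cost is a sentence or two of text and a tablet count at visits that patients already attend. The downside is small: some packs will not come back, and a returned count cannot tell a tablet taken from one thrown away, which is why the patient's report should stay.

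### The second primary outcome is a raw 48-week total of symptom days, with no rule for diaries that end when patients leave early

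*Combined protocol and SAP*

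**What the plan says.** The End Points section lists "total symptom days within the 48-week study period" as the second primary outcome. It is a count; no rate or denominator is given.

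The data come from diaries, described under Study Design and Randomization: "Each participant should complete diary cards during the study period", and "The participants are asked to hand in daily symptom records at each visit". Visits are monthly.

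The only method in the Statistics section that fits this outcome is Student's "t test for continuous variables", described as univariate. That section also sizes the trial "based on the proportion of patients who would discontinue the study prematurely because of unsatisfactory therapy", assuming "94% on-demand therapy continuation rate and 92% continuous therapy continuation rate", which implies exits of 6% and 8%. It allows a further 10% of non-evaluable patients without defining them. On-demand therapy is declared non-inferior "if the upper bound of the two-sided 90 % CI for the difference in proportions" lies below 10 percentage points.

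No section states an analysis set for symptom days, a minimum of diary completion, how a missing day counts, or what happens to the total of a patient who leaves early.

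**The concern.** A patient who leaves because therapy is unsatisfactory probably has more symptom days than one who stays. If the diary ends at exit, a raw total credits that patient with none afterwards. If the patient is excluded instead, a poorly controlled patient disappears from the comparison. Either way, one of the two primary outcomes would depend partly on when dissatisfied patients stop writing in a diary. With no rule stated, the handling could also be chosen after the results of this open-label trial are known.

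How many leavers stop their diaries is not clear. The Statistics section speaks both of leaving the study and of continuing therapy, and diaries are requested for the study period. The concern is therefore conditional on diaries ending at or near exit.

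**Working it through.** **The plan's own figure.** With continuation rates of 0.94 and 0.92, a margin of 0.10, one-sided 5% and 90% power:

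n = (1.645 + 1.282)² × (0.94×0.06 + 0.92×0.08) / (0.10 + 0.02)² = 8.564 × 0.130 / 0.0144 = 77.3, so 78 per arm. Power at 78 is 90.2%. Then 78/0.80 = 97.5, rounded to 98 per arm, or 196 in all. The stated figures reproduce. They imply 78×0.06 = 4.7 and 78×0.08 = 6.2 early exits.

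**Inputs for the illustration.** From the documents: 48 weeks = 336 days, exits of 6% and 8%, 78 per arm. Assumed, and the same in both arms: completers symptomatic on 15% of days, leavers on 60%, exit at week 16 (day 112), all leavers stop the diary, standard deviation (SD) 40 to 80 days.

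**Mean per arm,** with p the proportion leaving:
- full burden: (1−p)×0.15×336 + p×0.60×336
- raw total: (1−p)×0.15×336 + p×0.60×112
- leavers excluded: 0.15×336

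| Handling | On-demand (6%) | Continuous (8%) | Difference | Error |
|---|---|---|---|---|
| Full burden | 59.47 | 62.50 | −3.02 | – |
| Raw total | 51.41 | 51.74 | −0.34 | 2.69 |
| Leavers excluded | 50.40 | 50.40 | 0.00 | 3.02 |

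Here the error favours continuous therapy. If half of the leavers keep their diaries, the raw-total error is 1.34 days.

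**Against sampling error.** SE of the difference = SD×√(2/78) = 6.4 days (SD 40) or 12.8 days (SD 80). 2.69 days is 0.42 or 0.21 of that.

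**Sensitivity to the assumptions.** Each percentage point of difference in exits hides 0.01 × leaver rate × (336 − exit day). The base case gives 0.01×0.60×224 = 1.34 days. The range is 0.01×0.40×112 = 0.45 (40%, week 32) to 0.01×0.80×252 = 2.02 (80%, week 12). For the planned 2 points that is 0.9 to 4.0 days.

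**One patient.** At a leaver rate of 50% and exit at week 12, a full burden of 168 days is recorded as 42, below a completer's 50.4.

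**Timing can reverse the direction.** At a leaver rate of 50%, 8% leaving at day 300 lose 0.08×0.5×36 = 1.4 days per patient in the arm. Of the other arm, 6% leaving at day 84 lose 0.06×0.5×252 = 7.6. With continuous exits at week 24, the break-even is 0.06×(336−x) = 0.08×168, so x = 112: on-demand is understated more if its exits average before week 16.

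**A larger imbalance.** At 18% v 8% in the base case, the raw difference is 1.68 days and the full difference 15.12, an error of 13.4 days.

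**What rescaling recovers.** If leavers keep one rate throughout, days per recorded day restores the full difference. If they are at 15% for 56 days and 60% afterwards, with exit at day 112, a leaver records 8.4 + 33.6 = 42 days, rescales to 42×336/112 = 126, and has a full burden of 8.4 + 168 = 176.4. For 18% v 8% (10 points):
- raw: 0.10×(42 − 50.4) = −0.84
- rescaled: 0.10×(126 − 50.4) = 7.56
- full: 0.10×(176.4 − 50.4) = 12.6
- weeks 9–48 only: 0.10×(168 − 42) = 12.6

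**The case against.** The strongest reply is that the effect is small and bounded. At the only exit rates in the documents, the error is a fraction of a standard error and, in the base case, works against on-demand therapy, the regimen being tested for non-inferiority.

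The large example also cannot accompany a favourable result on the discontinuation criterion. At 18% v 8% the upper limit is 0.10 + 1.645×√(0.18×0.82/78 + 0.08×0.92/78) = 18.8%, well above 10%. With 8% continuous exits, the criterion passes only up to about 10.4% on-demand: 0.024 + 1.645×√(0.104×0.896/78 + 0.08×0.92/78) ≈ 0.100. That excess of 2.4 points hides 2.4×1.34 = 3.2 days (1.1 to 4.8 over the range above). Finally, the option to switch on-demand patients to continuous use may keep some treatment failures in follow-up.

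Most of this stands, and it limits the size. A reader might infer that the raw total conceals on-demand failures and so produces a false finding of non-inferiority. The documents do not support that: the stated criterion counts discontinuations directly.

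Three things remain. The bound assumes equal exit timing, which the plan does not give. The discontinuation criterion is not among the listed outcomes and does not correct the symptom-day comparison. And the switch option applies to one arm only, so retention may itself differ by arm.

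**Conclusion.** The concern holds as a missing rule on a primary outcome. As written, the plan lets an early end of the diary pass as absence of symptoms. In the base case the error is about 1 to 3 days at the planned exit rates. Truncation alone gives at most 2.7 days, or 0.2 to 0.4 of an assumed standard error. It becomes material only with less favourable assumptions: higher leaver rates, more unequal exits or different timing between arms.

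All symptom rates, exit times and SDs are assumptions, as is the proportion of leavers who stop their diaries. Confidence is high that no rule exists and moderate for direction and size.

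A reader might also infer that the diaries already planned are enough to eliminate the bias. They are not: nothing in the documents provides for diary days after a patient has left, so collected data can only reduce it.

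**What to change.** Amend the analysis plan before the data are examined:

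- Define the outcome as symptom days divided by recorded diary days, scaled to 336 days.
- Include all randomised patients in their assigned arm, switched patients among them, with a stated minimum of recorded days. Twenty-eight is natural, because patients already "report the number of esomeprazole tablets taken per 4-week period".
- Compare arms by a regression adjusting for the baseline GERDQ total, which is already collected. This gains precision but does not correct exit bias. At an assumed correlation of 0.2 to 0.5, variance falls by 4 to 25%, so 78 per arm acts like 78/0.96 = 81 to 78/0.75 = 104.
- Report by arm the recorded days and the number of patients below the minimum.
- Report the same measure for weeks 9–48, when the regimens differ. Keep the 48-week measure first: it is the stated period, and with a 28-day minimum the later window loses patients who leave before week 12.
- Add one sensitivity analysis assigning a range of high symptom rates (for example 40, 60 and 80%) to days after exit for unsatisfactory therapy, including patients below the minimum.

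The cost is wording; there are no new data items and the sample size is unchanged. There are three downsides. Short diaries are noisy: at a 60% rate and independent days, the SE of one scaled total is 336×√(0.24/28) = 31 days from 28 recorded days. The minimum drops the earliest leavers from the main analysis, which is why the counts and the sensitivity analysis are needed. And rescaling only partly corrects informative exit, recovering 7.6 of 12.6 days in the step-rate example.
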